1.4. Participating Sites: Gaborone CRS #31833 and Francistown CRS #31891

1.5. Study Design: This study will be a phase I/II, multi-site clinical trial of dual treatment with two broadly neutralizing monoclonal antibodies (bNAbs), VRC01LS and 10-1074, offered to HIV-1 infected virally suppressed children. There will be 4 Steps in the protocol: PK Step, Step 1, Step 2, and Step 3. In the PK Step, antiretroviral treatment (ART) is continued and 12 study participants will undergo safety and PK testing, 6 for each bNAb used in the study (10-1074 and VRC01LS). In Step 1, ART is continued and dual bNAb treatment occurs, with PK confirmation of dual bNAb dosing for the first 6 participants in Step 1. In Step 2, ART is withdrawn and dual bNAb maintenance treatment occurs. In Step 3, dual bNAbs will be discontinued and participants will be re-started on ART.

Figure 1: Study Schematic

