Following a successful Step 1 review, Step 2 may begin. Step 2 will begin after a participant has spent at least 8 weeks in Step 1. For the first 6 participants, Step 2 will begin at a scheduled bNAb dosing visit (i.e. 4 weeks from last Step 1 bNAb dosing), and for all subsequent participants it will begin at the 8 Week visit date for Step 1 (which becomes the Week 0 Step 2 visit). Participants with ongoing viral suppression throughout Step 1 will undergo withdrawal of ART and will continue maintenance 10-1074 (30mg/kg) and VRC01LS (10mg/kg) treatment for up to 24 weeks in Step 2. HIV-1 RNA will be checked at all visits in Step 2, which occur weekly from Weeks 1-4 in Step 2, and every 2 weeks thereafter. Qualitative HIV DNA will be checked at each visit by DBS. If a participant experiences a single viral rebound ≥ 400 copies/mL in Step 2, ART will be re-started (and VRC01LS and 10-1074 will be discontinued). A single viral rebound is defined as an HIV RNA result ≥ 400 copies/mL at any Step 2 visit, without need for confirmation. If HIV RNA becomes ≥ 400 copies/mL prior to the end of Step 2, all evaluations ordinarily scheduled at "Week 24" will be performed immediately prior to ART re-initiation. If HIV-1 RNA is ≥ 40 copies/mL but < 400 copies/mL, or if Qualitative DNA turns from negative to positive, virologic monitoring tests will be repeated weekly. Clinical examination will occur at each study visit.

Step 3 (all participants)

All participants will end Step 2 after 24 weeks, and enter Step 3. In Step 3, both 10-1074 and VRC01LS will be discontinued, and ART will be re-started. Follow-up visits in Step 3 will occur at 4,

12, and 24 weeks.

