6.6. Concomitant Medications: ART Management

During the PK Step, Step 1, and Step 3, ART will be provided as part of the Botswana ART program (Masa Program), but may be dispensed by study staff as per prior agreements between BHP and the Botswana Ministry of Health. ART is standard of care for HIV-infected children in Botswana and will not be considered study drug. At the time of enrollment, all children in this study will continue the ART regimen being provided through the EIT Study, and will re-start ART with that same regimen in Step 3

as long as there is no clinical contraindication. During the PK Step, Step 1, and Step 3, the ART regimen may be changed if required. All ART management decisions will be per Botswana ART guidelines and/or by study physicians made with guidance from specialists.

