13.8. Monitoring and Interim Analyses

An independent, external Safety Monitoring Committee (SMC) will be established for this study, consisting of approximately 5 members, and approved by the study sponsor. Committee members will include those with expertise in HIV treatment trials and pediatrics. The primary role of the SMC is to help protect the safety of participants in the study. The reviews of interim data by the SMC will be triggered by criteria described below, but will occur at least every six months unless otherwise recommended by the SMC. The SMC will make recommendations to the study team and to the study sponsor. Following SMC reviews, the sponsor and study team will communicate and discuss the findings. A response plan will be developed by the study team, and sign off by the sponsor will be required to implement the response.

13.8.1. Quarterly Reporting and SMC Triggers for Safety or Stopping Criteria. Monthly safety and accrual monitoring by the protocol team will occur throughout the study. Reports will be provided to the study sponsor and IRBs quarterly. Regularly scheduled conference calls will occur between members of the study team (including 1 or more PIs) and the Medical Officer at least quarterly. Serious adverse events that are EAEs may trigger an early review by the SMC (SAE-category EAE reporting will be used for most of the study). The occurrence of any EAE will prompt immediate review by the PIs and Medical Officer. The attribution of relationship of an EAE to study product will be discussed and the relationship will be determined by the study team, taking into account the site and the Medical Officer's assessment of the event. Interpretation of 10-1074 or VRC01LS relationship to adverse events will be based on the type of event, the relationship of the event to the time of immunization, the known biology of the monoclonal antibody and the investigators' medical judgment. Gradation of relationship will use the following terminology: "not related", and "related." The occurrence of 2 EAEs determined to be related to study product will trigger an SMC review. This may lead to a recommendation for study discontinuation in consultation with the study team and sponsor. Due to the fact that Grade 3 neutropenia and anemia are common in children on ARVs, and the fact that hemolyzed specimens may falsely lead to Grade 3 hyperkalemia values, these toxicities will not be counted in the real-time safety review algorithm.

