NOTE: If at any time during the study the triggers for SMC review are met, the study will be paused to new accruals and an SMC review performed within 7 days. The SMC will decide what additional data they would like to see and advise the study team on how to proceed.

Review of Data from PK Step

After all 12 PK Step participants complete the PK Step, safety, PK, and viral suppression data will be reviewed within 8 weeks by the study team including its sponsor representatives, and SMC. All PK

data from the PK Step will be assessed based on pre-specified PK trough targets; the study team will determine if median trough concentrations are above the pre-specified targets (see Section 2.8.1) and present this information in a written report to the SMC. In addition, outlier concentrations will be presented and reviewed; the study team expects no more than 2 participants to have trough concentrations below 115 mcg/mL for VRC01LS and no more than 2 participants to have trough concentrations below 5mcg/mL for 10-1074. The SMC and the study team will review any cases of outlier PK concentrations and make individual recommendations about whether a child with these levels should proceed to Steps 1-3. The SMC will review safety data utilizing pre-defined safety criteria defined as follows: 0 EAEs support study continuation; 1-2 EAEs related to study product but for different events warrant concern; >2 EAEs, or 2 of the same EAEs that are related to study product may lead to a recommendation for study discontinuation. If safety criteria are met, and if the PK data are in the pre-specified range (see Section 2.1.8), Step 1 will begin unless otherwise recommended by the SMC. If the dosing and frequency of bNAbs established in the PK Step is accepted, it will continue to be used for the first 6 participants in Step 1 (see additional safety review below). If a change in dosing is recommended by experts on the study team (or by the SMC, if it does not accept the team's recommendation), adjustments will occur and IRB and study sponsor approval will be sought regarding required protocol changes prior to starting Step 1. The recommendations by the study team or by the SMC may include early termination of the study, if warranted by the safety/PK data, or a re-design of the study as approved by the study sponsors and regulatory agencies.

Review of Safety and PK Data from Step 1 (first 6 participants)

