Safety, PK, and viral suppression data for the first 6 Step 1 participants will be reviewed within 8 weeks by the study team including its sponsor representatives, and SMC. All PK data will be assessed by the study team based on pre-specified PK trough targets which are the same as those used in the PK Step. The review will confirm that PK targets are met during dual bNAb administration. Safety criteria for the Step 1 data will be reviewed by the SMC, using similar criteria as for the PK Step: 0 EAEs support study continuation; 1-2 EAEs related to study product but for different events warrant concern; >2 EAEs, or 2 of the same EAEs that are related to study product may lead to a recommendation for study discontinuation. If safety criteria are met, and if the PK data are in the pre-specified range (see Section 2.1.8), unless otherwise recommended by the SMC, the first 6 participants will enter Step 2 and enrollment of additional participants into Step 1 will continue. If the PK data are in range and no dosing changes for the bNAbs are required, the dosing will continue to be used for the remainder of the study unless new data emerges requiring additional review. If a change in dosing is recommended by experts on the study team (or by the SMC, if it does not accept the team's recommendation), IRB and study sponsor approval will be sought regarding required protocol changes. The recommendations by the study team or by the SMC may include early termination of the study, if warranted by the safety/PK data, or a re-design of the study as approved by the study sponsors and regulatory boards.

Review for Early Stopping Criteria in Step 2

The SMC will review safety and virologic outcome data every six months after the first participant enters Step 2 or on a frequency recommended by the SMC, but at least annually. During Step 2, as well as a possible early review triggered by the occurrence of EAEs as outlined above, early review by the SMC will be triggered if 2 participants are unable to achieve re-suppression of HIV-1 RNA to <40 copies/mL within 12 weeks after re-starting ART. Otherwise, time to re-suppression will be reported to the SMC as part of their regular reviews.

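### The exclusion of Grade 3 neutropenia and anaemia from real-time safety review rests on ARV use, yet it is not limited to periods on ART and so reaches Step 2

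*Protocol*

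**What the plan says.** Protocol Section 13.8.1 sets the early safety trigger: "The occurrence of 2 EAEs determined to be related to study product will trigger an SMC review". A few lines later it explains an exclusion: "Due to the fact that Grade 3 neutropenia and anemia are common in children on ARVs", and because haemolysed specimens can falsely suggest Grade 3 hyperkalaemia, "these toxicities will not be counted in the real-time safety review algorithm". So neutropenia and anaemia share one reason, ARV use, and hyperkalaemia has a different one.

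The note that follows begins "If at any time during the study the triggers for SMC review are met", and provides for a pause to new accrual and an SMC review within 7 days. The subsection on early stopping in Step 2 keeps the same trigger: "During Step 2, as well as a possible early review triggered by the occurrence of EAEs as outlined above".

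On treatment, Section 1.5 states: "In Step 2, ART is withdrawn and dual bNAb maintenance treatment occurs". Section 1.7 gives the duration as up to 24 weeks. ART is not a study agent in any Step: "ART is standard of care for HIV-infected children in Botswana and will not be considered study drug" (Section 6.6).

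**The concern.** The rule is wider than its reason. ARV-related cytopenia is a plausible background problem in the PK Step, Step 1 and Step 3, when children take ART. In Step 2 they do not, yet the exclusion continues.

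Step 2 is also the only part of the trial in which haematological effects of the two antibodies can be observed without concurrent ARVs. Section 13.4.1.3 acknowledges that few children had received VRC01LS and none had received 10-1074. At stake is whether a related Grade 3 neutropenia or anaemia EAE in that period counts towards bringing the SMC in early, either as one of two such events or alongside one related EAE of another kind.

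**Working it through.** The plan states no operating characteristics for the two-EAE trigger, so there is no figure to reproduce. The check is mainly a reading of the text.

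**Does the exclusion reach Step 2?**

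| Question | Source | Answer |
|---|---|---|
| Why are the two cytopenias excluded? | 13.8.1 | Common in children on ARVs; no other reason |
| Is the exclusion limited by Step or ART status? | 13.8.1 | No |
| When does the trigger apply? | 13.8.1, note | At any time in the study |
| Is it restated for Step 2? | 13.8.1, Step 2 stopping criteria | Yes, by reference back, with the exclusion not lifted |
| Are children on ART in Step 2? | 1.5, 1.7 | No |
| Do the amendments narrow it? | Letter of Amendment 2, item 14; purposes of Letter of Amendment 3 | No; the first revises only the Step 1 data review, and no stated purpose of the second concerns this exclusion |

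Blood counts are taken in Step 2 (Section 7.7.1 lists haematology at Weeks 6, 10, 14, 18 and 22), so such events could be detected.

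**What must happen for an event to fall in the gap?** The trigger counts EAEs. Under Section 8.2.2 these are SAE-category events plus listed serum sickness, hypersensitivity and injection-site events. The event must therefore be a neutropenia or anaemia of Grade 3 (Grade 4 is not excluded), qualify as an EAE, be judged related, and occur in Step 2.

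**How much exposure is affected?** Section 5.5 anticipates 20 to 36 children. If all enter Step 2 and complete 24 weeks:

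- 20 × 24/52 = 9.2 child-years
- 36 × 24/52 = 16.6 child-years

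These are ceilings, because a child who rebounds to 400 copies/mL or more leaves Step 2 early. At the 30% success rate used in Sections 10.1.2 and 13.8.1, completers alone would contribute 0.30 × 9.2 = 2.8 to 0.30 × 16.6 = 5.0 child-years. Children who rebound would add part-time to that.

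**Illustration only.** No event rate is given. Let p be an assumed chance per child of a related Grade 3 neutropenia or anaemia EAE in Step 2. If such events counted, the chance of at least two affected children among n would be 1 − (1 − p)^n − n·p·(1 − p)^(n−1):

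| Assumed p | n = 20 | n = 36 |
|---|---|---|
| 2% | 0.060 | 0.162 |
| 5% | 0.264 | 0.543 |
| 10% | 0.608 | 0.887 |
| 20% | 0.931 | 0.997 |

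The documents do not support any particular row. Since a qualifying event must be both an EAE and related, the higher rates are upper-end cases. On the natural reading, the contribution under the present text is zero at any p.

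**The case against.** The strongest objection is that the algorithm is never defined. Hyperkalaemia is excluded in the same sentence because of spurious specimens, which suggests a filter on graded laboratory values. On that reading a serious, related cytopenia might still count, and the only fault would be an undefined term. This stands as a real ambiguity. The position of the sentence, just after the two-EAE trigger, favours the other reading, and either way the text needs a definition.

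Second, other oversight remains:

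- All AEs of Grade 1 or higher are recorded (8.2).
- Any EAE gets immediate review by the PIs and Medical Officer, and the team monitors safety monthly (13.8.1).
- The SMC reviews data about every six months and can alter its own triggers. In Step 2 it may choose another frequency, but at least annually (13.8.1).
- The SAP summarises Grade 3 or higher, serious and bNAb-related AEs without this exclusion (4.2.2).

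All of this stands. A reader might infer that these events are hidden; they are not. What may be lost is the automatic early SMC review and accrual pause. The routine interval of about six months is close to the whole 24-week Step 2 period, so it is not a full substitute.

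Third, a reader might infer that a cytopenia in Step 2 must be due to the antibodies. The documents do not support that. Residual ART effects and repeated blood draws remain possible causes, and neutropenia in the infant VRC01 study was not attributed to VRC01 (2.1.7). But the trigger already requires a judgement of relatedness, which can deal with these causes without a blanket exclusion.

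**Conclusion.** The point holds as a narrow mismatch between a rule and its reason. The ARV justification does not cover Step 2, apart from residual ART effects early on, and no available text limits the exclusion to periods on ART. The practical consequence depends on reading the algorithm as the two-related-EAE trigger, which is natural but not certain.

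The exposure affected is at most 9.2 to 16.6 child-years for 20 to 36 children, and less with early rebound. This measures exposure, not effect. With no event rate in the documents, the number of missed or delayed SMC reviews cannot be estimated, and it may be zero.

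Two stronger readings should be avoided. One is that two related events of any other kind would call the SMC: they must be EAEs, and Grade 3 hyperkalaemia is excluded too. The other is that the antibodies become the only study treatment in Step 2: they are the only study agents in every Step, and what changes in Step 2 is that ART is withdrawn. This is a cheap improvement to safety oversight, not a defect that undermines the trial.

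**What to change.** In Section 13.8.1:

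1. State that the real-time safety review algorithm is the trigger of two EAEs judged related to study product.
2. Limit the neutropenia and anaemia exclusion to events with onset on ART (PK Step, Step 1, Step 3). In Step 2 they then count when they are EAEs judged related, with carry-over from prior ART and blood draws weighed in that judgement. The hyperkalaemia exclusion can stay, since haemolysis does not depend on ART.
3. If the exclusion is meant to apply in Step 2 as well, give a reason that holds off ART.

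The cost is a few words and possibly an extra SMC review with a short accrual pause.

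SAP Version 2 (Section 4.1.3) describes Step 2 in the past tense. If Step 2 is complete, the useful change is in reporting: list Grade 3 neutropenia and anaemia with onset in Step 2 separately, with relatedness, among children who entered Step 2. The AE summaries in SAP Section 4.2.2 specify no split by Step, so this would be one added table using data already collected.

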13.9. Biohazard Containment

As the transmission of HIV and other blood-borne pathogens can occur through contact with contaminated needles, blood, and blood products, appropriate blood and secretion precautions will be employed by all personnel in the drawing of blood, infusing antibodies, and shipping and handling of all specimens for this study, as currently recommended by the Centers for Disease Control and Prevention.

All infectious specimens will be sent using the ISS-1 SAF-T-PAK or equivalent package that is compliant to the International Air Transport Association Dangerous Goods Regulations Packing Instruction 602. Please refer to individual carrier guidelines (for example: Federal Express, Airborne, etc.) for additional specific instructions. Appropriate shipping permits will be obtained.

13.10. Vertebrate Animals

This project does not involve vertebrate animals.

14. ADMINISTRATIVE PROCEDURES

14.1. Protocol Registration

Prior to implementation of this protocol, and any subsequent full version amendments, the protocol and the protocol informed consent forms will be approved by the IRBs in Botswana and in Boston, and any other applicable regulatory entity. Upon receiving final approval, investigators will submit all required protocol registration documents to the DAIDS Protocol Registration Office (PRO) at the

DAIDS Regulatory Support Center (RSC). The DAIDS PRO will review the submitted protocol registration packet to ensure that all of the required documents have been received. Site-specific informed consent forms will be reviewed and approved by the DAIDS PRO, and sites will receive an Initial Registration Notification from the DAIDS PRO that indicates successful completion of the protocol registration process. A copy of the Initial Registration Notification should be retained in the site's regulatory files.

Upon receiving final IRB/EC and any other applicable regulatory entity approval(s) for an amendment, sites should implement the amendment immediately. Sites are required to submit an amendment registration packet to the DAIDS PRO at the RSC. The DAIDS PRO will review the submitted protocol registration packet to ensure that all the required documents have been received. Site-specific ICF(s) WILL NOT be reviewed and approved by the DAIDS PRO and sites will receive an Amendment Registration Notification when the DAIDS PRO receives a complete registration packet. A copy of the Amendment Registration Notification should be retained in the site's regulatory files.

For additional information on the protocol registration process and specific documents required for initial and amendment registrations, refer to the current version of the DAIDS Protocol Registration Manual, which is available on the RSC website: <https://rsc.niaid.nih.gov/clinical-research-sites/daids-protocol-registration-policy-and-procedures-manual>.

14.2. Regulatory Oversight

This study will be sponsored by the National Institute of Allergy and Infectious Diseases (NIAID) which is part of the United States National Institutes of Health (NIH). The study product VRC01LS is provided by the NIAID Vaccine Research Center (VRC). The study product 10-1074 is provided by the Division of AIDS (DAIDS). DAIDS within the NIAID will be responsible for regulatory oversight of this study. DAIDS will distribute safety-related information pertaining to the study products prior to and during the conduct of the study, in accordance with its sponsor obligations.

An IND application to the Division of Antiviral Drug Research, Center for Drug Evaluation and Research (CDER), FDA, will be submitted. To support the IND application, the investigator brochure for VRC-HIVMAB080-00-AB (VRC01-LS) and 10-1074 will be submitted to the FDA. These documents include all relevant information on physical, chemical and pharmaceutical properties of the study drugs, summarize results from non-clinical and clinical studies and list all toxicology and safety data. Cross-reference to the existing IND for VRC01LS (held by DAIDS) and 10-1074 (held by Rockefeller University) will also occur for the IND application of this clinical trial.

14.3. Study Implementation

This study will be conducted in accordance with the protocol, international good clinical practice guidelines, and all applicable US, and non-US country and local regulations. Study implementation will also be guided by SOPs. These SOPs will be updated and/or supplemented as needed to describe roles, responsibilities, and procedures for this study.

14.4. ClinicalTrials.gov

This protocol will be subject to the United States Food and Drug Administration Amendments Act of 2007 (FDAAA), including registration in ClinicalTrials.gov.

## Version History

Version	Changes Made	Date Finalized
1	Original Version	10/27/2021
2	

Clarified primary safety outcome as occurring through 30 days after the last study visit (this aligns with the intended outcome measure as posted on clinicaltrials.gov).

Revised plans for exploratory analysis evaluating characteristics of participants who experienced virologic rebound during Step 2 versus participants who did not experience rebound.

Edits for clarification.

	09/27/2022

